## PROTOCOL TITLE: Proof-of-Concept Trial of a Positive Psychology Intervention for Caregivers of Patients with Hematologic Malignancies Undergoing Hematopoietic Stem Cell Transplantation

patient transplant consent visit) are completed in the pre-transplant phase and to speak with the study interventionist, a trained CRC, weekly. Immediately after the completion of each exercise, participants will rate the ease of exercise completion, overall utility of the exercise, and their current levels of positive affect. After the Week 9 intervention phone session, participants in Phase-2 will repeat self-assessment questionnaires completed at baseline either over the phone, in-person at a routine clinic visit, or via a REDCap survey link emailed to participants. Additionally, participants will be asked to complete a recorded exit interview over the phone. These individual, semi-structured exit interviews will elicit feedback about the intervention (e.g., relevance and applicability of the chosen PP exercises, intervention length, timing, and delivery), study procedures, and the questionnaires. Exit interviews will be recorded, transcribed, coded and thematically analyzed. With the Oppenheimer Grants Program funding, participants who complete study procedures will receive \$100 renumeration for their time and feedback. At study completion, we will inquire about participants' potential interest in being contacted about our future studies.

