## 7.0 Study Timelines\*

Table 1. Expected Study Timeline:

Time Point	Table 1: Study Procedure
Months 0-2	Finalize protocol development and submit to Institutional Review Board for approval.
Months 3-4	Staff Training ❖ Train CRC in study procedures, recruitment, data collection and intervention delivery.

**PROTOCOL TITLE: Proof-of-Concept Trial of a Positive Psychology Intervention for Caregivers of Patients with Hematologic Malignancies Undergoing Hematopoietic Stem Cell Transplantation**

Months 5-12	Open Pilot and One-Arm Feasibility study: ❖ Enroll 5 caregivers to the open pilot trial to provide feedback for intervention refinement. ❖ Enroll 20 caregivers to the one-arm feasibility trial.
Months 9-15	Data Collection: ❖ Complete baseline data collection within a week of participant enrollment. (Only for Phase-2 participants) ❖ Conduct 9-week PATH intervention via telephone. ❖ At the 9-week period, complete exit interviews.
Months 15-18	Data Analysis: ❖ Complete data analysis and submit primary manuscripts. ❖ Prepare and submit grant proposal for efficacy study.

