## **9.0 Procedures Involved\***

### **9.1 Study Design**

The proposed project entails two phases. Phase one is an open-pilot trial in 5 caregivers of patients undergoing HSCT to refine the PATH intervention. Phase two is one-arm trial evaluating the feasibility and acceptability of the PATH intervention in 20 caregivers of patients undergoing HSCT. All participants will be approached in person during patient's HSCT hospitalization or during a patient's routine clinic visit anytime up to the 100-day post-transplant period, or with patient permission over the phone if caregiver is not physically present at the consent visit for eligibility determination. Interested participants will be screened based on the inclusion/exclusion criteria and verbal consent would be obtained (via phone).

Upon consent to participate in the study, participants in Phase-2 will be asked to complete baseline questionnaires either in-person, over the phone, or via a REDCap survey link to participants. After baseline assessments are completed, participants will be given an intervention manual with 9-weekly PP exercises and an explanation of the exercises and intervention.

Participants in Phase-1 will complete the intervention after consenting for the study. All participants in Phase-2 will be asked to complete the 9-weekly PP exercises starting after the baseline questionnaires (i.e., after the

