**Weekly phone sessions for positive psychology intervention:** All participants will be asked to complete the 9 weekly PP exercises and to speak with the interventionist weekly. Weekly phone sessions will last approximately 15-20 minutes. Prior to completing each phone session, participants will be asked to rate their current level of happiness and optimism, using a 10-point Likert scale. Immediately after completing the exercise and phone session, participants will rate the ease of exercise/session completion, overall utility of the exercise/phone session, and their current levels of happiness and optimism, all using 10-point Likert scales. These calls will be recorded so that a percentage (10%) of these recordings can be reviewed by [name], to ensure that the PP intervention is being delivered as described in the protocol. Given the results of our prior PP studies in medical populations yielding a 64-85% completion rate of the exercises, our recent proof-of-concept trial (18-225) yielding 100% completion rate among HSCT recipients, and that this is a feasibility study (i.e., we want to assess participants' willingness to complete the phone sessions), we will expect participants to complete at least 6 PP exercises. In other words, if a participant completes at least 6 sessions, missed sessions will not be considered a deviation from the protocol.

**Follow-up assessments:** At Week 9, participants will repeat self-assessment questionnaires obtained at the beginning of the study either in-person, during a routine follow-up clinic visit, over the phone, or via a REDCap survey link e-mailed to them, depending on participant's preference. A week prior to intervention completion, participants will be mailed the Actigraph GT3X+ for follow-up physical activity data collection and participants will mail back the Actigraph in prepaid envelopes we will provide. Furthermore, participants will be asked to provide feedback about the program via a recorded exit interview over the phone.

**Positive Psychology Program Content:** All phone sessions will include (a) a review of the ease and utility of the week's PP exercise, (b) a discussion of the rationale of the next week's PP exercise through a guided review of the PP manual, and (c) assignment of the next week's PP exercise. During the calls, the interventionist and participant will also review the next section of the treatment manual and prepare for the upcoming week's exercise.

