## **10.0 Data and Specimen Banking: Not Applicable**

### *10.1. Data analysis*

We will use descriptive statistics (e.g., mean) for continuous variables and proportions for categorical variables to summarize the demographic and clinical characteristics of caregivers enrolled in the study.

**Specific Aim 1 (Phase 1: Intervention Refinement): To refine a positive psychology intervention, PATH, in caregivers of HSCT recipients based on findings from an open-pilot study.** Informed by our prior work, our planned sample size (N=5) will allow us to obtain comprehensive feedback about the intervention for refinement. The qualitative exit interviews will explore the following themes: 1) caregiver perception of intervention content; 2) barriers/challenges with the delivery method; and 3) modifications to promote caregiver engagement. All exit interviews will be recorded, transcribed, coded, and thematically analyzed using a directed content analysis. Findings from phase-1 will be used to refine and finalize the intervention for feasibility testing in phase 2. Participant feedback of the study assessments/questionnaires will also help to refine the study procedures for the phase-2 of this project.

**Specific Aim 2 (Feasibility and Acceptability): To assess the feasibility and acceptability of the PATH intervention for caregivers of patients undergoing HSCT.** Based on prior work, we define feasibility as >60% of eligible participants enrolling for the study and >60% of enrolled participants who start the intervention completing at least 6 of the 9 PP sessions, consistent with metrics used in prior positive psychology feasibility trials and other behavioral intervention studies. We will estimate the feasibility using the proportion who meet the criteria, and we will place an exact 95% binomial confidence interval around the proportion. We will assess acceptability using weekly ratings of ease and utility of each exercise (0=very difficult/not helpful; 10=very easy/very helpful). The mean ease and utility of each exercise will be calculated, and we will use a threshold mean combined score of 7.0/10 for acceptability that was used in prior studies.

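### The exit interview is timed only at week 9, so the interview feedback of caregivers who stop or withdraw earlier may be lost from phase 1 refinement and from the phase 2 qualitative work.

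*Combined protocol and SAP*

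**What the plan says.** Three places in the protocol time the exit interview.

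- **Section 7.0, Table 1:** "At the 9-week period, complete exit interviews".
- **Section 9.1:** "After the Week 9 intervention phone session, participants in Phase-2 will repeat self-assessment questionnaires", and the next sentence is "Additionally, participants will be asked to complete a recorded exit interview over the phone".
- **Section 9.7, under the week-9 follow-up assessments:** "Furthermore, participants will be asked to provide feedback about the program via a recorded exit interview over the phone".

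Section 9.4 describes the interview guide and a length of about 30 minutes, but gives no time point and no rule for early leavers.

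Section 10.1 gives the interviews their role in Aim 1: "The qualitative exit interviews will explore the following themes: 1) caregiver perception of intervention content; 2) barriers/challenges with the delivery method". The third theme is changes that would promote engagement. The same section says that "our planned sample size (N=5) will allow us to obtain comprehensive feedback about the intervention for refinement". In phase 2 the qualitative data explore acceptability, content and delivery preferences.

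Section 3.1 says that caregivers who withdraw are not replaced, in either phase. Section 12.0 says that a caregiver who withdraws will be asked for the reason, if comfortable giving it, and states the purpose as checking for adverse events. Section 11.0 adds that refusals are recorded and that reasons for dropout are reviewed weekly.

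**The concern.** A caregiver who leaves in week 3 has first-hand knowledge of what made the programme hard to continue. The interview themes ask about exactly that, yet the plan contains no step at which this caregiver would be interviewed. Payment follows completion of study procedures (sections 9.1 and 24.0), so a leaver also has no stated incentive to give feedback later.

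Two pieces of evidence are at stake. The first is the phase 1 refinement, where five caregivers shape the manual taken into phase 2. The second is the phase 2 qualitative account of acceptability and delivery preferences, which is meant to inform a later efficacy trial. In both, the interviews would come only from caregivers still in the study at week 9.

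Some early stopping is foreseeable from the protocol itself. Section 11.0 calls refusal of later sessions a threat to the study, and section 17.0 expects that some of the patients may die during the study or within months of it.

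**Working it through.** The plan states no figure on this point, so there is none to reproduce. The check has two parts.

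**1. Which evidence does an early leaver still supply?**

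- *Exit interview:* none is scheduled before week 9 (7.0, 9.1, 9.7).
- *Weekly ease and utility ratings:* taken after each exercise (9.1, 9.7), so those given before stopping exist. A caregiver who stops after two weeks supplies two of nine sets. The 7.0/10 acceptability criterion in 10.1 rests on these ratings.
- *Feasibility proportion:* 10.1 counts caregivers who start and complete at least 6 of 9 sessions, so a starter who leaves stays in the denominator.
- *Reason for stopping:* requested and reviewed (11.0, 12.0), but as part of withdrawal and safety monitoring. Section 10.1 does not assign it to the thematic analysis or to refinement.

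The gap is therefore in the interview evidence, and the recorded reasons fill it only in part.

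**2. How many interviews could be lost?**

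Inputs from the protocol: 5 caregivers in phase 1; 20 in phase 2; no replacement; exercise completion of 64% to 85% in prior studies in medical populations and 100% in the prior trial in transplant recipients (9.7).

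The protocol gives no rate at which caregivers leave before week 9. Let q be that rate. As an assumption, I take q = 0, 0.15 and 0.36, the complements of 100%, 85% and 64%. Those figures describe exercises completed by patients, so they only indicate a range. Caregivers are treated as independent.

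- Share of phase 1 interviews removed by one leaver: 1/5 = 20%.
- Expected leavers in phase 1, 5q: 0; 0.75; 1.8.
- Chance of at least one leaver in phase 1, 1 − (1 − q)^5:
  - q = 0: 0
  - q = 0.15: 1 − 0.85^5 = 0.556
  - q = 0.36: 1 − 0.64^5 = 0.893
- Expected leavers in phase 2, 20q: 0; 3.0; 7.2.

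**The case against.** The strongest reply is that the interview is not conditional on finishing the programme. Week 9 is a study time point. The interview sentence in 9.1 refers simply to participants, and 9.7 foresees missed sessions without withdrawal. A caregiver who skips sessions but stays in the study can be interviewed at week 9. This stands, and it limits the point to caregivers who stop taking part or withdraw.

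It is also fair to say that leavers are heard in other ways. Each weekly call reviews the ease and utility of the exercise, sessions are recorded, the team meets weekly to solve delivery problems, and reasons for dropout are kept. These sources are real. However, the ratings do not explain why someone stopped, and the recordings are planned for fidelity review.

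The completion reported in the prior transplant-recipient trial was 100%. If caregivers match it, nothing is lost. Those participants were patients, so the evidence is indirect.

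A reader might infer four stronger claims that the documents do not support:

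- *That leavers vanish from the acceptability evidence.* The formal criterion uses ratings that they gave before stopping, and section 12.0 allows withdrawn participants' data to be analysed.
- *That the interviews are the only data for Aim 1.* They are the main named qualitative source; the weekly calls and ratings also exist.
- *That 7 of 20 interviews could be lost because 13 of 20 passes the rule of more than 60%.* The 7 are caregivers below six sessions, if all 20 start. One with five sessions may be interviewed, and one with seven may leave before week 9, so the count does not measure lost interviews.
- *That the acceptability conclusion is shown to be biased favourably.* Selection of the interviewees is plausible, but the documents give no data on how leavers' views differ, so neither its direction nor its size can be stated.

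**Conclusion.** The point holds as a limited gap in the qualitative evidence. Every place that times the exit interview puts it at week 9, and none provides one at early stopping or withdrawal. Followed as written, the plan may lose early leavers' interview feedback on barriers and engagement in both phases. It matters most in phase 1, where each loss is one fifth of the interviews.

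The range of 56% to 89% for at least one loss among the five depends wholly on the assumed leaving rates of 15% to 36%; at a rate of zero there is no loss. The 7.0/10 acceptability decision and the feasibility proportion are not affected through the interviews. This is a worthwhile, inexpensive improvement and not a flaw in the primary criteria.

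**What to change.** - In 9.1, 9.4, 9.7 and Table 1, offer the existing voluntary phone interview to every caregiver who starts the intervention: at the time of stopping for early leavers, and at week 9 for the rest.
- In 10.1, include the recorded reasons for dropout in the qualitative analysis.
- Report how many completers (at least 6 of 9 sessions) and non-completers were interviewed. Describe themes by completer status in phase 2 only. Splitting five caregivers in phase 1 could leave one person in a group, which adds little and risks identifying that person.

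The cost is small. The staff and guide are already in place, and the total cannot exceed the one interview per caregiver already foreseen (25 × 30 minutes = 12.5 hours). At the upper assumed leaving rate, the interviews to be recovered number 25 × 0.36 = 9, or 4.5 hours of calls. Some leavers will decline, so the gap will narrow but may not close.

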### 9.2 *The PATH Intervention*

After the initial phone visit to introduce the concept of positive psychology and the PATH intervention, participants will be asked to complete 9 weekly positive psychology exercises with the study interventionist over the phone.

**Table 2. PP intervention component:** modules and exercises. Intervention content will be customized to HSCT context.

Module 1: Gratitude/positive affect-based exercises		
Week 1	Gratitude for positive events 	Participants identify three positive events that have occurred in the past week and reflect on their feelings as they recall and describe these events.
2	Gratitude letter 	Participants write a letter of gratitude thanking a person for their support or kindness.
3	Gratitude skills application	Participants select a useful activity from the prior two weeks, consider how to adapt the activity to daily life, and develop a plan to utilize this skill regularly.
Module 2: Strengths-based exercises		
Week 4	Recalling past success 	Participants recall an event in which they experienced success, then write about the event, their contribution to the success, and positive feelings elicited by recalling it.
5	Using personal strengths 	Participants undergo a brief assessment of personal strengths, then find a specific new way to use one of their 'signature strengths' in the next 7 days.
6	Strength-based skills application	Participants select a useful activity from the prior two weeks, consider how to adapt the activity to daily life, and develop a plan to utilize this skill regularly.
Module 3: Optimism and meaning-based exercises		
Week 7	Enjoyable and meaningful activities 	Participants complete three activities: an enjoyable activity alone, an enjoyable activity with another person, and a meaningful activity completed alone or with others.
8	The good life 	Participants imagine and write in detail about a best possible (realistic) future one year from now and consider small short-term steps to take toward such a future.
9	Skills application + future planning	Participants select an activity from this module and develop a plan to utilize this skill—and additional skills from the program—this week and beyond

As shown in Table 2 above, the PATH intervention will focus on three main modules: 1) gratitude/positive affect-based exercises; 2) strengths-based exercises; and 3) optimism and meaning-based exercises.

- **Training:** The PP exercises for this trial have been identified via published literature, or directly from researchers, and from our prior work (17-154 and 18-225) in HSCT recipients. Additional text outlining the rationale and instructions for each exercise are in the written packets for each exercise that are

## PROTOCOL TITLE: Proof-of-Concept Trial of a Positive Psychology Intervention for Caregivers of Patients with Hematologic Malignancies Undergoing Hematopoietic Stem Cell Transplantation

provided to participants. [name] and CRCs will engage in several training exercises prior to study initiation. [name] has substantial experience in delivering PP exercises from prior work which will inform the training of other study team members. [name] will also review the treatment manual and the team's prior training manuals related to these exercises.

- **Ensuring Fidelity of the PATH Intervention:** We will take several measures to ensure the fidelity of our study design and intervention delivery. (Table 3) For the study design, we will use a well-established intervention guide, utilized in prior studies by our group, and pilot-tested in patients undergoing HSCT (18-225). Also, we will use rigorous training procedures for our CRCs. To ensure fidelity of the intervention delivery, the [name] will meet weekly with the CRCs to provide ongoing training on effective and consistent delivery of positive psychological exercises to participants and will help to problem-solve issues as they come up during the intervention delivery. We will audio-record all sessions and use a fidelity structure developed from prior work to measure the extent to which domains of each session are addressed. On a monthly basis, [name] will independently review (and rate for fidelity, using an adapted scale) a random sample of 10% of the audio-recorded sessions to ensure intervention fidelity.

Table 3: Fidelity	Steps Taken to Ensure Fidelity	Fidelity Assessment
Study Design	

- Intervention based on extensive literature review and prior work in several medical populations

- Standard intervention dose with clear feasibility data based on prior work

	

- Utilize evidence-based positive psychology intervention guide based on prior trials

- Measure number of intervention visits

Intervention Delivery	

- Utilization of prior tested positive psychology intervention guide with standardized content areas

- Audio-record all intervention calls and sessions

	

- Study PI, [name] and interventionist (CRC) will meet for ongoing training of consistent intervention delivery

- [name] will help problem-solve issues as they come up during the intervention delivery

- On a monthly basis, [name] will independently review (and rate for fidelity, using an adapted scale) a random sample of 10% of the audio-recorded sessions to ensure intervention fidelity

### 9.3 Selection of Instruments

While the primary aim of this study is to refine the intervention and assess its feasibility, we will also determine the feasibility of study procedures, including administering study assessments at baseline and at the end of the intervention for future efficacy studies. During phase 1, we will utilize feedback from participants regarding the length of the assessment battery and revise the assessments incorporated in phase 2. In Phase 2, we will then assess the feasibility and acceptability of completing the assessment battery. Study instruments were selected based on their appropriateness for measuring the important outcomes pertinent to caregivers in this population. All measures were used in prior studies and demonstrated strong psychometric properties. All measures are valid, reliable, and frequently used within cancer patient and caregiver populations.

The demographic questionnaire will ask study participants to provide their email address to allow us to email study assessments if preferred. If participants do not have an email address, we will either send them paper copies of the survey or ask them to complete them verbally over the telephone. We will track the methods of survey completion among participants. The entire study assessment battery will take approximately 15-20 minutes to complete.

## PROTOCOL TITLE: Proof-of-Concept Trial of a Positive Psychology Intervention for Caregivers of Patients with Hematologic Malignancies Undergoing Hematopoietic Stem Cell Transplantation

### Self-reported measures:

- **Demographic questionnaire:** Participants will self-report their age, sex, race/ethnicity, marital status, relationship satisfaction, religion, and education level, relationship status, relationship to the patient, and living situation [Appendix F].
- **QOL:** We will use the CareGiver Oncology QOL questionnaire (CarGOQOL) to measure caregiver QOL [Appendix G].
- **Caregiving burden:** We will use the Caregiver Reaction Assessment (CRA) to assess caregiving burden [Appendix H].
- **Mood:** We will use the Hospital Anxiety and Depression Scale (HADS) to assess symptoms of depression and anxiety in all study participants [Appendix I].
- **Self-efficacy:** We will use the Cancer Self-Efficacy Scale-transplant (CASE-t) to measure caregivers' confidence in managing the impact of HCT [Appendix J].
- **Perceived coping skills:** We will use the Measure Of Current Status (MOCS) to assess caregivers' self-perceived status on skills targeted by the intervention including ability to relax, recognizing stress-inducing situations, restructuring maladaptive thoughts, and coping [Appendix K].
- **Optimism:** We will use the 10-item Life Orientation Test-Revised (LOT-R) to measure dispositional (trait) optimism. Higher scores indicate greater optimism. [Appendix L]
- **Positive Affect:** We will use the 10-item Positive and Negative Affect Schedule (PANAS) to measure positive affect; higher scores indicate greater positive and negative affect. [Appendix M]
- **Satisfaction:** We will use the 5-item Satisfaction with Life Scale (SWLS) to measure satisfaction with life; higher scores indicate greater satisfaction with life. [Appendix N]
- **Gratitude:** We will use the 6-item Gratitude Questionnaire to measure dispositional gratitude; higher scores indicate greater proneness to experience gratitude in daily life. [Appendix O]
- **Purpose and Flourishing:** We will use the 8-item Flourishing Scale to assesses a person's self-perceived success in critical areas such as engagement, relationships, self-esteem, meaning & purpose, and optimism; higher scores indicate many psychological resources and strengths. [Appendix P]
- **Physical activity:** We will use the well-validated Actigraph GT3X+ accelerometer, for 7 days of wear; minimum acceptable use is 4+ days with 10+ hours of recorded data as in prior guidelines to measure minutes/day of light activity (100-1951 counts/min) along with sedentary leisure time (SLT), given their links to health outcomes [Appendix Q]. Participants in Phase-2 will be given the actigraph either in person at a routine clinic visit or via mail for a 7-day wear by participants prior to the initiation of the intervention. Prior to the end of the intervention at week-8, participants will receive the actigraphs again for follow-up data collection during the last week of the intervention.

